Quality of Life After Interventional Thyroid Treatment (DSR)

Study Identifier NCT03880578

Date 2019-04-13

Study Protocol

Objectives. Aim of the study is to evaluate the quality of life (QoL) in patients with subclinical hyperthyroidism undergoing interventional thyroid treatment, particularly radioiodine treatment (RIT), compared to a control group of euthyroid subjects.

Design. Study design is monocentric, prospective and controlled, comparing two groups of patients, Group 1 comprised of consecutive patients with subclinical hyperthyroidism referred to our department for interventional treatment and Group 2, serving as a control, euthyroid patients presenting at fixed intervals for surveillance of non-toxic nodular goitre. For the intervention, randomised allocation and blinding are not possible, and necessity of intervention is determined independently of the study. The original design included a surgical group with similar characteristics to the RIT group. Due to early problems with the follow-up of surgically treated patients, a decision has been made to conduct the study with two groups only.

Eligibility criteria are adult women or men, aged 18 to 80 years, without any comorbidity or drug use that could potentially interfere with their thyroid function tests and QoL measures. Children and older patients are excluded. Further exclusion criteria are the presence or suspicion of low-T3 syndrome, pregnancy and an inability or unwillingness to provide informed consent. The study aims to recruit 50 patients per group, based on a power analysis conducted prior to the study.

Diagnosis and treatment modality are confirmed and determined prior to and independently of the study.

Study visits were scheduled at baseline, i.e. prior to the intervention in group 1), and 6 months and possibly 12 months thereafter.

The pre-specified primary study end point is a change in the composite score of the ThyPRO quality of life questionnaire between the control group and RIT group before and after intervention. Secondary endpoints include subcategories of the QoL responses, hormonal changes, thyroid structural parameters, thyroid volume, and their relationship with QoL measures.

Methods. QoL was measured with the internationally validated thyroid-specific quality of life questionnaire ThyPro (German version). Thyroid hormones FT3, FT4 and TSH were measured by routine laboratory methods. Thyroid volume was estimated by ultrasonography of the thyroid gland.

Statistical analysis plan. Change over time between groups is assessed with a repeated-measures mixed-effects model. Fixed effects include group (intervention vs control), visit (time point), and the interaction of visit and group (group by visit), the random effect is the subject level. In dealing with missing visits missingness at random (MAR) is assumed. Mean adjusted differences (MAD) between groups over time are reported, based on the interaction term group by visit in the mixed model. A two-sided p value of <0.05 is considered indicative of statistical significance. All analyses are performed in the R statistical programming environment.

Informed Consent

Written informed consent is obtained from each study participant. The protocol has been approved by the Ethics Committee of the University of Duesseldorf, Germany (No. 2018-278-KFogU) and preregistered. The consent form is available upon request in German (original) and English translation.

Funding

The study is investigator initiated. No funding or sponsoring has been received.

Declaration of interest

There is no conflict of interest to report.

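### A subject-only random effect reads as a random intercept; if the optional 12-month visit is modelled, standard errors for single-visit differences can be wrong

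*Combined protocol and SAP*

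**What the plan says.** The Statistical analysis plan states: "Change over time between groups is assessed with a repeated-measures mixed-effects model". The fixed effects are group, visit and group by visit. On the dependence between visits it adds only that "the random effect is the subject level". No random slope, residual correlation structure, visit-specific variance or robust standard error is named.

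The result to be reported is described as follows: "Mean adjusted differences (MAD) between groups over time are reported, based on the interaction term group by visit in the mixed model". On incomplete follow-up: "In dealing with missing visits missingness at random (MAR) is assumed". The test level is two-sided 5%.

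The Study Protocol section schedules visits at baseline and "6 months and possibly 12 months thereafter". Nothing says whether 12-month data enter the model. The same interaction term carries the primary endpoint, the change in the ThyPRO composite score.

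**The concern.** A random intercept for subject implies equal variances at all visits and the same correlation between any two of them. With three visits, the fit pools all within-subject variation into one residual variance and uses it for both the 0–6 and the 0–12 month group-by-visit contrasts. With equal visit numbers, the two contrasts get exactly the same standard error. With fewer 12-month visits the standard errors differ because the numbers differ, but the averaged variance underneath is unchanged.

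Change may well vary more over one interval than the other. The second contrast spans twice the time of the first, and one group is treated just after baseline. If so, at least one visit-specific standard error is wrong, and its confidence interval and p value are too narrow or too wide. Because the plan relies on MAR, a wrong covariance can also affect the estimates themselves when visits are missing; that effect was not quantified here.

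**Working it through.** **Inputs from the documents.** 50 per group; visits at 0, 6 and possibly 12 months; two-sided 5%; MAR. No ThyPRO SD, within-subject correlation or rate of missing visits is given, and the inputs to the power analysis are not shown. The plan therefore has no figure of its own to reproduce on this point. Every covariance and missing rate below is an assumption.

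**Formulas, complete data, three visits.** Let S1 and S0 be the 3×3 covariance matrices in the RIT and control groups, H the 3×3 centring matrix, and c = (−1, 1, 0) for 6 months or (−1, 0, 1) for 12 months.

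- Residual variance under the random intercept: s² = trace(H S)/2, averaged over the two groups
- Model variance of either contrast: 2 s² (1/50 + 1/50)
- True variance: c′S1c/50 + c′S0c/50
- SE ratio = √(model variance / true variance)
- Type I error = 2Φ(−1.96 × ratio)

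With SD 1 throughout and the same matrix in both groups, s² = 1 − (mean of the three correlations).

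**Worked example, correlations 0.7 (0–6), 0.7 (6–12), 0.5 (0–12).**

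- Mean correlation 1.9/3 = 0.633, so s² = 0.367
- Model variance for both contrasts: 2 × 0.367 × 0.04 = 0.0293, SE 0.171
- True variance at 6 months: 2 × (1 − 0.7) × 0.04 = 0.024, SE 0.155
- True variance at 12 months: 2 × (1 − 0.5) × 0.04 = 0.040, SE 0.200
- Ratios 1.106 and 0.856, giving type I errors of 3.0% and 9.3%

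**All scenarios** (correlations in the order 0–6 / 6–12 / 0–12; SD 1 unless stated):

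| Assumed covariance | SE ratio, 6 mo | SE ratio, 12 mo | Type I error, 6 mo | Type I error, 12 mo |
|---|---|---|---|---|
| 0.7/0.7/0.6 | 1.054 | 0.913 | 3.9% | 7.4% |
| 0.7/0.7/0.5 | 1.106 | 0.856 | 3.0% | 9.3% |
| 0.8/0.8/0.64 | 1.125 | 0.839 | 2.7% | 10.0% |
| RIT 0.5/0.75/0.5; control 0.7 throughout | 0.946 | 0.946 | 6.4% | 6.4% |
| Both groups 0.5/0.75/0.4 | 0.949 | 0.866 | 6.3% | 9.0% |
| RIT 0.4/0.7/0.4; control 0.7/0.7/0.6 | 0.962 | 0.913 | 5.9% | 7.4% |
| RIT SD 1/1.3/1 at 0/6/12 months; correlation 0.6 | 0.971 | 1.067 | 5.7% | 3.7% |
| Equal SDs, correlation 0.6 throughout (reference) | 1.000 | 1.000 | 5% | 5% |

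The seven rows above the reference are not limits. Two further assumed patterns, simulated with 40,000 trials each, gave 2.3% and 10.8% (0.8/0.8/0.6) and 8.0% and 7.9% (0.5/0.8/0.5).

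**Simulated type I error, random intercept against a common unstructured matrix** (REML, Satterthwaite degrees of freedom; 20,000 trials per scenario with complete data, 5,000 with missing visits; range over scenarios):

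| 12-month visits | Random intercept, 6 mo | Random intercept, 12 mo | Unstructured, 6 mo | Unstructured, 12 mo |
|---|---|---|---|---|
| Complete | 2.7–6.6% | 3.7–10.3% | 4.8–5.4% | 4.8–5.2% |
| 20% missing | 3.0–6.1% | 3.4–10.1% | 4.5–5.5% | 4.8–5.4% |
| About 33% missing, depending on the 6-month score | 3.1–6.2% | 3.9–9.6% | 4.6–5.3% | 4.5–5.6% |
| 50% missing | 3.3–5.8% | 4.0–9.6% | 4.6–5.3% | 4.8–6.1% |

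With 5,000 trials, the Monte Carlo standard error near 5% is √(0.05 × 0.95/5000) = 0.3 percentage points. Under the random intercept, the 12-month model SE was 1.00 times the 6-month SE with complete data, 1.08–1.09 times with 20% missing, 1.16–1.17 with about 33% and 1.30–1.32 with 50%. The reduced numbers thus widen the 12-month interval, but the misstated variance remains.

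**Where the problem does not arise.** With baseline and 6 months only and complete data, the interaction test is the two-sample t test on change scores, so the SE ratio is 1. Simulation with unequal correlations or SDs between groups and 0% or 20% of 6-month visits missing gave 4.8–5.4%. With three visits, the joint 2-df group-by-visit test ran at 4.8–5.9% with complete data and 4.5–6.2% with missing visits.

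**The case against.** The case against has five parts.

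- **The conditions are not established.** The 12-month visit is only possible, and the primary endpoint compares before with after, which is naturally a two-visit comparison that the model handles well. This stands, and it is why the point is conditional. But the schedule allows a third visit and the plan does not keep it out of the model.
- **The random intercept is inferred.** In R, a subject random effect can be combined with a residual correlation structure, and the repeated-measures label might hint at one. None is named, however, so a random intercept remains the plain reading. If something else is intended, one sentence settles it.
- **The scenarios were chosen.** Milder departures do little: by the same formula, 0.7/0.7/0.65 gives 4.4% and 6.2%, and 0.6/0.65/0.6 gives 5.5% at both visits. Several entries are conservative. This stands: the tables show what is possible, not what is likely in this trial.
- **The natural test of the interaction is the joint one.** That test is largely unaffected. But the plan reports differences over time as well, and those visit-specific intervals are exposed.
- **The remedy has a price when many 12-month visits are missing.** With half missing, the unstructured matrix gave 4.8–6.1% at 12 months, and 5.8% against 5.3% when the random intercept was true. This also stands. The excess is small beside the random intercept's upper end of 9.6% in the same setting.

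**Conclusion.** The concern holds as a conditional one. If three visits are modelled with a random intercept and single-visit differences are reported, their standard errors are right only when the variances of change over the intervals are equal. In the seven assumed scenarios with complete data, the 6-month SE ran from 5% too small to 13% too large, and the 12-month SE from 16% too small to 7% too large. Neither size nor direction can be known for this trial, because the documents give no SDs or correlations. The joint interaction test and a two-visit analysis are essentially unaffected. The change is worth making because it is cheap and the covariance is unknown in advance; the plan has not been shown to give a wrong answer. Confidence is medium.

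**What to change.** State in the Statistical analysis plan whether the 12-month visit enters the model. If it does, specify an unstructured within-subject covariance across visits, common to both groups, in place of the random intercept. Fit it by REML with Kenward-Roger or Satterthwaite degrees of freedom, that is, as a mixed model for repeated measures in R. If only baseline and 6 months are modelled, the random intercept can stay.

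A separate matrix per group should be at most a sensitivity analysis, if 12-month numbers allow. It did no better at 12 months: 5.3–6.7% with about 33% missing and 5.1–6.5% with 50% missing. Testing at two visits also raises a multiplicity question, which needs its own rule.

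The cost is one or two sentences, with the same data and software. The model estimates 6 covariance parameters instead of 2, and its 12-month tests may be slightly liberal if half of those visits are missing.

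### Does reporting group differences through the group-by-visit interaction leave the comparison with euthyroid controls unanswered?

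*Combined protocol and SAP*

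**What the plan says.** The Objectives paragraph states the aim: "Aim of the study is to evaluate the quality of life (QoL) in patients with subclinical hyperthyroidism undergoing interventional thyroid treatment". It singles out radioiodine among the treatments and sets these patients against euthyroid controls. The primary endpoint is "a change in the composite score of the ThyPRO quality of life questionnaire between the control group and RIT group before and after intervention".

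The statistical analysis plan opens by saying that a repeated-measures mixed model will assess how the groups differ in change over time. On the terms of that model it says "Fixed effects include group (intervention vs control), visit (time point), and the interaction of visit and group (group by visit", with a random effect for subject. The reporting sentence is "Mean adjusted differences (MAD) between groups over time are reported, based on the interaction term group by visit in the mixed model".

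On the visits: "Study visits were scheduled at baseline, i.e. prior to the intervention in group 1), and 6 months and possibly 12 months thereafter". On allocation: "For the intervention, randomised allocation and blinding are not possible, and necessity of intervention is determined independently of the study". The surgical group has been dropped, so only one pair of groups can be compared.

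**The concern.** The reporting sentence can be read in two ways. Its first half suggests a gap between the groups at each visit. Its second half, the tie to the interaction, suggests a difference in change from baseline. These are different quantities, and the plan does not define the abbreviation further, name a visit or mention confidence intervals.

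If only the interaction were shown, a reader would learn whether the gap to controls had moved but not how much of it was left. The same coefficient arises whether treated patients reach the controls' quality of life or stay well short of it. A null interaction likewise cannot separate patients who never had a deficit from patients whose deficit persisted. Because the controls are euthyroid, a reader will naturally ask whether treated patients reach their level.

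A second strand concerns causal reading. Attributing the interaction to radioiodine assumes that both groups would have changed equally without it, and a single pre-treatment visit cannot test this.

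**Working it through.** **1. The plan's own figure.** The only figure is 50 patients per group, from a prior power analysis. It cannot be reproduced, because no effect size, SD or power is given. With two-sided alpha 0.05 (from the plan) and assumed powers, a comparison of two means at n = 50 per group detects (1.96 + 0.842) × √(2/50) = 0.56 SD at 80% power and (1.96 + 1.282) × √(2/50) = 0.648 SD at 90%. This does not reveal which contrast was powered.

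**2. What the planned model contains.** Take visit as categorical, with controls and baseline as reference:

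- group coefficient = difference at baseline
- interaction at visit t = difference in mean change from baseline to t
- difference at visit t = group coefficient + interaction at t

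All three come from the one model in the plan.

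**3. Does the interaction fix the remaining gap?** The check used simulated data with assumed values: 50 per group, three visits, subject and residual SD both 0.7, and a true effect of -0.8 at both follow-ups. The same random errors were used for three true baseline gaps.

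| True baseline gap | Group coefficient | Interaction, 6 months | Sum = gap at 6 months |
|---|---|---|---|
| 0 | 0.060 | -0.917 | -0.857 |
| 0.8 | 0.860 | -0.917 | -0.057 |
| 1.6 | 1.660 | -0.917 | +0.743 |

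So the interaction alone does not give the gap. The gap is nevertheless obtained by adding two coefficients of the planned fit.

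**4. Precision of the two contrasts.** Assume unit SD, complete data and n = 50 per group. The pre-post correlation ρ is also assumed.

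- Interaction: SE = √(2(1-ρ) × 2/n) = 0.200, 0.155 and 0.126 for ρ = 0.5, 0.7 and 0.8. The 95% half-widths are about 0.40, 0.31 and 0.25 SD.
- Gap at one visit: SE = √(2/n) = 0.200, half-width about 0.40 SD.

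The gap is estimated no more precisely than the change once ρ is 0.5 or more, so making it the headline contrast would gain nothing there.

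**5. Does the planned contrast match the endpoint?** The endpoint is a change, compared between two groups, before versus after intervention. With baseline as reference, that is the interaction coefficient. The plan's opening sentence also speaks of change over time between groups. Read together, the difference in change is the natural meaning of the reporting sentence.

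**6. Would tightening the wording be neutral?** A rewrite would have to name a visit, and 6 months is the obvious candidate. The plan does not say whether the test is one coefficient or, if 12 months is held, a joint test on 2 degrees of freedom. Assume ρ = 0.7 at every pair of visits, n = 50 per group, a true interaction of -0.35 SD at 6 months and large-sample tests:

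- 6-month coefficient alone: 0.35/0.155 = 2.26, power about 62%.
- Joint test: each contrast has variance 0.024 and their covariance is 0.012. With an equal effect at 12 months the noncentrality is 0.35² × (2/3)/0.012 = 6.8, power about 64%. With a doubled effect at 12 months it is 0.35² × 2/0.012 = 20.4, power about 99%.

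Fixing the visit is therefore a new decision that could alter the test. It is not a matter of wording alone.

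**The case for a change.** The strongest case for changing the plan is that the fix is cheap. Defining the term, listing the baseline and follow-up gaps with confidence intervals, and warning that a non-significant gap is not equality would need no new model and no extra p value. With a half-width of about 0.40 SD, an interval for the 6-month gap could easily include zero while a real deficit remained, so the warning has substance.

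Part of this stands. The term is not defined as a list of contrasts, the primary visit is not named, and the interaction does not show the remaining gap. Unit-level means or gaps by visit with intervals would make the report more useful.

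The step from there to a needed change does not stand. The plan nowhere restricts reporting to one number, and it makes no claim of equality with controls that would need guarding. Recovery to euthyroid level is a reasonable clinical question, but the aim does not state it. The equal-change assumption is a limitation of a non-randomised comparison, and the protocol already discloses the absence of randomisation and the nature of the controls. Nothing in the documents shows that the assumption fails, and a sentence about it belongs in the report's discussion.

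It also adds nothing to count how often the two contrasts would differ in significance. They are tests of different parameters with different true values, so differing is expected and does not measure an error in this trial.

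**Conclusion.** No change to the plan follows. Followed as written, it estimates the difference in change in the ThyPRO composite between the two groups, which is the pre-specified primary endpoint. The gap at each visit comes from the same fit as the group coefficient plus the interaction. An analyst would ordinarily present it alongside the main result, with intervals.

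The size of the matter is a definitional gap: no figure in the plan is wrong and no better method is on offer. The conclusion rests on two readings: that the reporting sentence means the difference in change, which the plan's opening sentence and the endpoint both support, and that the aim sets no separate target for the level reached. If the trial meant to claim that treated patients attain euthyroid quality of life, the interaction would not support that claim, but the documents make no such claim.

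The unnamed primary visit is real missing detail. It concerns timing, not the choice between level and change, and 6 months is the only follow-up scheduled without qualification. The SDs, correlations, effects and baseline gaps above are assumptions, because the documents give none.
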